Study Protocol

Title:

Effects of Taurine Supplementation on Repetitive Sprint Performance and Exhaustion Time in College Students Under High-Temperature and High-Humidity Conditions

Protocol ID:

No. 2021A43

Date:

January 9, 2025

1. Background

High-temperature and high-humidity environments (defined as ambient temperature \geq 35°C and relative humidity \geq 60%) adversely affect sports performance by increasing the body's heat load and impairing thermoregulation. These conditions lead to earlier fatigue, reduced performance, and increased physiological strain. Recovery after exhaustion is critical in such conditions for enhancing subsequent performance.

Taurine, a sulfur-containing amino acid, has shown promise in enhancing sports performance, improving calcium regulation in muscles, reducing oxidative stress, and mitigating fatigue under extreme environmental conditions. Previous studies have highlighted taurine's benefits, but the effects of different taurine doses in repetitive sprint (RS) exercises after exhaustive exercise in high-temperature and high-humidity conditions remain unclear. This study aims to investigate these effects in college students.

2. Objectives

Primary Objective:

To examine the effects of acute pre-exercise taurine supplementation at different doses (6g, 4g, 1g) on RS performance and endurance following exhaustive exercise in high-temperature and high-humidity environments.

Secondary Objectives:

- To analyze the impact of taurine on physiological indicators, such as heart rate (HR) and blood lactate (BLA).
- To measure subjective sensations using the rating of perceived exertion (RPE).
- To evaluate recovery performance through reverse vertical jump height.

3. Study Design

Design:

- Single-blind, randomized, crossover-controlled experimental design.
- Four groups: High-dose taurine (6g), Medium-dose taurine (4g), Low-dose taurine (1g), Placebo (0g).
- Each subject participated in four trials, one for each group.

Environment:

• Temperature maintained at 32±1°C and relative humidity ≥60%, using a heating system (SAWO, Finland) and humidification system (BELIN, China).

Participants:

- 16 college students (8 male, 8 female) from Capital University of Physical Education and Sports.
- Inclusion Criteria:
 - 1. Aged 18–28 years.
 - 2. No exercise-related risk as indicated by the PAR-Q questionnaire.
 - 3. No taurine-based supplementation in the past month.

Experimental Process:

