- Pre-exercise taurine/placebo ingestion (6g, 4g, 1g, or placebo).
- RS test (6 sprints, 10 seconds each, with 10-second recovery intervals).
- Measurements: Peak Power (PP), Mean Power (MP), Fatigue Index (FI), HR, BLA, RPE, and exhaustion time (ET).

4. Experimental Procedure

- 1. Warm-Up:
 - o 5-minute steady-state cycling at 100W.
 - o Measurement of reverse vertical jump height.
- 2. Exhaustive Exercise Test:

- Cycling test to exhaustion, starting at 50W and increasing by 50W every 3 minutes at 60 RPM.
- Exhaustion determined by cadence drop or inability to maintain resistance.

3. Rest and Recovery:

 20-minute recovery period with periodic measurements of HR, RPE, and BLA.

4. Repetitive Sprint Test (RS):

 Six maximal sprints (10 seconds each) with resistance set at 7.5% of body weight.

5. Measurements

- Sports Performance Indicators: PP, MP, FI (recorded for each sprint).
- Endurance and Recovery Indicators: ET, reverse vertical jump height.
- **Physiological Indicators**: HR and BLA (monitored pre-, post-exercise, and during recovery).
- **Subjective Indicators**: RPE assessed at pre-defined intervals.

6. Statistical Analysis

- Data analyzed using SPSS 27.0.
- Normality tested using the Shapiro-Wilk test.
- Repeated measures ANOVA (group × time) for performance indicators.
- Paired-samples t-tests for pre- and post-test comparisons.
- Significance level set at P<0.05.

7. Ethical Considerations

- Study approved by the Institutional Ethical Committee of Capital University of Physical Education and Sports, Beijing, China (No. 2021A43).
- Informed consent obtained from all participants.

Statistical Analysis Plan

Title:

Statistical Analysis Plan for the Effects of Taurine Supplementation on RS Performance in High-Temperature and High-Humidity Environments

Protocol ID:

No. 2021A43

Date:

January 9, 2025

1. Objectives

- Analyze the effects of different taurine doses on RS performance metrics (PP, MP, FI).
- Assess endurance and recovery indicators (ET, reverse vertical jump height).
- Investigate physiological responses (HR, BLA) and subjective fatigue (RPE).

2. Statistical Software

• SPSS Version 27.0.

3. Data Analysis Methods

- 1. Descriptive Statistics:
 - \circ Means \pm standard deviations calculated for all variables.
- 2. Normality Test:
 - Shapiro-Wilk test to check for normal distribution.
- 3. Primary Analysis:
 - Repeated measures ANOVA for group × time interaction effects on PP, MP, FI, HR, BLA, and RPE.

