- 4. Secondary Analysis:
 - Paired-samples t-tests for reverse vertical jump pre- and post-exercise comparisons.

o One-way ANOVA for ET across groups.

5. Effect Sizes:

o Partial eta-squared (η^2 partial): 0.01 (small), 0.06 (medium), 0.14 (large).

4. Data Presentation

- Line graphs for repeated measures (PP, MP, FI, HR, BLA, RPE).
- Bar charts for pre- and post-test comparisons (reverse vertical jump).

5. Significance Criteria

• Statistical significance set at P<0.05.

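### At n = 16, the SAP's fixed partial eta-squared labels would call a null within-subject effect at least 'medium' about 42% to 50% of the time, so they say little about effect size.

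*Combined protocol and SAP*

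**What the plan says.** The whole effect-size rule is one line in SAP section 3, item 5: partial eta-squared, with labels "0.01 (small), 0.06 (medium), 0.14 (large". It gives no bias-adjusted version and no confidence interval, and the plan has no estimated difference between a dose and placebo. Means and standard deviations are planned as descriptives (SAP section 3, item 1).

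Protocol section 3 sets the design to which the rule applies: "16 college students (8 male, 8 female"; "Four groups: High-dose taurine (6g), Medium-dose taurine (4g), Low-dose taurine (1g), Placebo (0g"; and "Each subject participated in four trials, one for each group". The sprint test is described there as "RS test (6 sprints, 10 seconds each, with 10-second recovery intervals", and protocol section 5 has PP, MP and FI recorded for each sprint.

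The SAP's primary analysis is "Repeated measures ANOVA for group × time interaction effects on PP, MP, FI, HR, BLA, and RPE". Exhaustion time is handled under the secondary analysis: "One-way ANOVA for ET across groups". The only decision criterion is in SAP section 5: "Statistical significance set at P<0.05".

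**The concern.** Sample partial eta-squared cannot be negative, so chance variation alone pushes it above zero. How far depends on the degrees of freedom, and in a within-subject design with few participants it is a long way relative to these cut-offs. Fixed labels ignore this. If the value expected from noise sits at the 'medium' boundary, 'medium' tells the reader almost nothing about how much taurine changes performance.

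What is at stake is how results are described. The primary objective is to examine the effects of three doses. A reader told that a non-significant dose effect was 'medium' may take that as a hint of benefit, when the value is what no effect would typically produce. An omnibus index also cannot show which dose differs from placebo, in which direction, or by how much.

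**Working it through.** The documents give no sample-size calculation or target effect, so there is no planned figure to reproduce.

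**Inputs.** n = 16, four dose levels and six sprints (protocol section 3); cut-offs 0.01, 0.06 and 0.14 (SAP section 3, item 5); alpha 0.05 (SAP section 5). The number of time points for HR, BLA and RPE is not stated; I assume 2 to 8.

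**Null distribution.** With no effect, normal errors and sphericity, partial eta-squared follows Beta(df1/2, df2/2), with mean df1/(df1 + df2). For an effect whose factors are all within-subject, df2 = df1 × (n − 1), so the mean is 1/n whatever the number of time points:

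- Dose: 3/(3 + 45) = 0.0625.
- Dose × sprint: df1 = 3 × 5 = 15, df2 = 15 × 15 = 225, and 15/240 = 0.0625.

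**Results with no true effect.** The last column is the smallest value that reaches P<0.05.

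| Test | df | Mean | Median | P(≥0.01) | P(≥0.06) | P(≥0.14) | Minimum at P<0.05 |
|---|---|---|---|---|---|---|---|
| Dose, within-subject | 3, 45 | 0.0625 | 0.051 | 0.928 | 0.421 | 0.076 | 0.158 |
| Dose × sprint, within-subject | 15, 225 | 0.0625 | 0.060 | >0.999 | 0.501 | 0.0025 | 0.102 |
| ET, one-way, 64 values taken as independent | 3, 60 | 0.0476 | 0.038 | 0.895 | 0.291 | 0.028 | 0.121 |
| Group × sprint, group entered as between-subject | 15, 300 | 0.0476 | 0.046 | >0.999 | 0.216 | <0.001 | 0.078 |

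For dose × time with 2 to 8 time points, P(≥0.06) runs from 42% to 52%. With sex as a between-subject factor, the null mean for dose becomes 3/(3 + 42) = 0.067.

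**Simulation check.** In 10,000 null data sets (16 participants, 4 doses × 6 sprints), the dose main effect averaged 0.063 and reached 0.06 in about 42%. The interaction averaged 0.062 to 0.063 and reached 0.06 in 50% with independent errors and 47% with serially correlated errors.

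**Link to the significance rule.** F = [η²/(1 − η²)] × df2/df1. At η² = 0.06, F = (0.06/0.94) × 15 = 0.957 for both within-subject tests, giving p = 0.42 (3, 45) and p = 0.50 (15, 225).

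**Effect of bias adjustment.** Partial epsilon-squared is df1(F − 1)/(df1·F + df2). An observed 0.0625 (F = 1) becomes 0.000, and 0.06 becomes −0.003. An observed 0.14 (F = 2.442) becomes 3 × 1.442/(3 × 2.442 + 45) = 0.083.

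**Exhaustion time.** Four values come from each person. If a one-way ANOVA is run as written, positive within-subject correlation inflates the error term and lowers the null index. By simulation, a correlation of 0.5 gives a mean of 0.025 and P(≥0.06) of 7%; a correlation of 0.8 gives 0.011 and 0.3%.

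**The case against.** The strongest reply is that these are conventional magnitude labels and that significance is judged separately. That is right, and it limits the point in several ways.

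- A reader might infer that the plan will present null dose effects as real. The documents do not support that. No rule treats a label as evidence, P<0.05 stands as its own criterion, and a value near 0.06 clearly fails it. Calling a non-significant result 'medium' is something the plan permits, not something it prescribes.
- A reader might infer that every significant result would be 'large', so that the labels carry no information. That holds only for the within-subject dose main effect (minimum 0.158), which the SAP does not name as a test although the same ANOVA yields it. A significant dose × sprint interaction needs 0.102 and a significant ET test 0.121; either may be 'medium'. Under the null, the interaction is labelled 'large' only 0.25% of the time.
- A reader might infer that noise is always called 'medium'. The null mean exceeds the cut by only 0.0025, and the median is at or below about 0.06 for the two tabulated within-subject tests. The label is close to a coin flip, not a certainty.
- Readers will also see dose means and SDs in original units. What the plan lacks is the paired difference from placebo with its interval.

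What remains is that fixed cut-offs on an uncorrected index are poorly calibrated for the planned interaction test at this sample size.

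**Conclusion.** The point holds as a reporting weakness of low severity. Under no effect, partial eta-squared averages 0.0625 in the within-subject analyses, and a label of 'medium' or above appears in about 42% (dose) to 50% (dose × sprint) of cases. The tests and their type I error are untouched.

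The size rests on complete data, near-sphericity, and both factors being within-subject, as the crossover implies but the SAP does not state. If group were entered as between-subject, the null mean would be 0.048, with 22% of null group × sprint effects labelled at least 'medium'. For ET under the planned one-way ANOVA, the mean is at most about 0.048 and the share at most 29%, assuming within-subject correlation is not negative.

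**What to change.** In SAP section 3, item 5, remove the three labels and substitute wording such as:

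> For each dose versus placebo, the effect size is the within-participant mean difference in original units with its 95% confidence interval. The summary is the mean over the six sprints for PP, MP and FI; the single value for ET; and [a named time point, or the mean over named time points] for HR, BLA and RPE.

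The bracketed choice must be filled in before analysis; otherwise the summary could be selected after seeing the data. These differences do not describe the group × time interaction. If a variance-explained index is kept for it, report bias-corrected partial omega-squared or epsilon-squared with its confidence interval, without size labels.

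The cost is a change of SAP wording, with no new data. The downside is slightly less direct comparability with papers that use the conventional labels.

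### The SAP's primary analysis tests six outcomes at an unadjusted 5% level with no primary outcome named, three of them secondary in the protocol, and gives exhaustion time a test that does not reflect the crossover

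*Combined protocol and SAP*

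**What the plan says.** **Threshold.** SAP section 5 states "Statistical significance set at P<0.05", and protocol section 6 says the same: "Significance level set at P<0.05". Neither document gives an adjustment, a testing order or a rule for declaring success.

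**SAP roles.** Under Primary Analysis, SAP section 3 item 3 plans "Repeated measures ANOVA for group × time interaction effects on PP, MP, FI, HR, BLA, and RPE". Item 4, Secondary Analysis, covers the jump-height comparison and a one-way ANOVA of ET across the groups. SAP section 1 lists its aims without ranking them.

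**Protocol roles.** The primary objective (section 2) concerns the effect of taurine dose "on RS performance and endurance following exhaustive exercise in high-temperature and high-humidity environments". The secondary objectives cover HR and BLA as physiological indicators, RPE as the subjective measure, and jump height as the recovery measure.

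**ET.** The protocol title begins "Effects of Taurine Supplementation on Repetitive Sprint Performance and Exhaustion Time in College Students", and section 5 has the line "Endurance and Recovery Indicators: ET, reverse vertical jump height". The SAP's title mentions RS performance but not exhaustion time.

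**Design.** Protocol section 3 describes a crossover in which 16 students each complete all four conditions (6 g, 4 g, 1 g, placebo).

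**The concern.** With six results under the primary label and no rule for which one counts, a reader of the final report cannot tell whether the study met its primary aim. An isolated HR or RPE finding could be presented as primary although the protocol ranks those measures second, and the 5% level would not apply to a claim picked from six.

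ET faces the opposite risk. It appears in the protocol title and is labelled an endurance indicator, yet it is placed in the secondary tier. Its test, as worded, would leave the differences between subjects in the error term, so a real effect on ET is more likely to be missed.

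**Working it through.** The documents state no overall error rate, power or sample-size calculation, so there is no figure of theirs to reproduce.

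**1. Roles side by side**

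| Outcome | Protocol objective | SAP section 3 |
|---|---|---|
| PP, MP, FI | primary (RS performance) | primary |
| HR, BLA, RPE | secondary | primary |
| Jump height | secondary | secondary |
| ET | primary if it is the endurance measure; wording unclear | secondary |

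The mismatch is partial. It is definite for HR, BLA and RPE, and open for ET.

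**2. Chance of at least one false positive among the six**

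Inputs: six tests (SAP section 3 item 3), each at 0.05 (SAP section 5). Assumptions: any one result may be claimed, and each test holds its level.

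- Independent outcomes: 1 − 0.95^6 = 0.265.
- Upper bound under any dependence: 6 × 0.05 = 0.30.
- Correlated outcomes: null simulation of six interaction F-tests with 16 subjects, four conditions and six time points, giving (4 − 1)(6 − 1) = 15 and 15 × 15 = 225 df, sphericity holding, 40,000 runs. The correlations are assumed, and so are six time points for every outcome.

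| Common correlation | At least one false positive |
|---|---|
| 0 | 26.4% |
| 0.3 | 24.8% |
| 0.5 | 22.4% |
| 0.7 | 17.8% |
| 0.9 | 11.8% |

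Moving HR, BLA and RPE out does not settle the matter. PP, MP and FI unadjusted give 1 − 0.95^3 = 14.3%, and adding ET gives 1 − 0.95^4 = 18.5%, both under independence.

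**3. ET analysed by a between-subjects one-way ANOVA**

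Inputs: 16 subjects × 4 conditions (protocol section 3). Take total variance 1 and an assumed within-subject correlation ρ, equal for all pairs of conditions. With no effect:

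- The condition mean square has expectation 1 − ρ.
- The one-way error mean square pools subjects (15 df) and residual (45 df), with expectation [15(1 + 3ρ) + 45(1 − ρ)]/60 = 1.

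The F ratio is therefore centred near 1 − ρ, not near 1, and the test rejects too rarely. Power is taken at the effect for which the repeated-measures ANOVA (3 and 45 df) has 80%, that is, noncentrality 11.90.

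| ρ | Rejection with no effect (nominal 5%) | Power, one-way | Power, repeated-measures |
|---|---|---|---|
| 0.3 | 1.4% | 62% | 80% |
| 0.5 | 0.3% | 39% | 80% |
| 0.7 | 0.02% | 11% | 80% |

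**The case against.** **ET is not clearly a primary outcome.** The objective speaks of endurance after exhaustive exercise. In protocol section 4 the test to exhaustion is step 2 and the sprints are step 4. If ET is the duration of step 2, it is not measured after exhaustive exercise, and the SAP title leaves it out. On the other side stand the protocol title and the endurance label in section 5. A reader might infer that the SAP has demoted a primary outcome. The texts do not settle that; they need reconciling.

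**26.5% is not the trial's error rate.** A reader might take it so. It needs independent outcomes, which is implausible for measures from the same people and sessions, and a rule that any one result may be claimed, which the documents do not state. This stands, but even at a correlation of 0.9 the rate is more than twice 5%.

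**Non-sphericity might seem to push the six-outcome rate higher still.** The documents do not support a figure for that. Only PP, MP and FI are recorded sprint by sprint; the number of time points for HR, BLA and RPE is not given. The SAP's silence on sphericity does not mean that no correction will be made.

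**The tested effect is already stated.** True for the six outcomes: it is the group × time interaction.

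**One-way ANOVA could mean one within-subject factor.** This cannot be excluded. The between-subjects reading is likelier, because the SAP specifies repeated measures for the other six outcomes and not for ET.

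**Section 3 may be ordered by method, not by outcome role.** Possibly, but then no primary outcome is named at all.

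**Conclusion.** The point holds in this form. Six outcomes share the primary label at an unadjusted 5%, no primary outcome or success rule is named, and HR, BLA and RPE are ranked above their protocol role. If any one may be claimed and each test holds its level, the error is 26.5% under independence, about 25% to 12% at correlations of 0.3 to 0.9, and never above 30%. The correlations, and six time points for every outcome, are assumptions.

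ET's role is unresolved between the documents, not demonstrably wrong. Its planned test, on the likelier reading, is too conservative: it does not inflate false positives, but it loses 18 to 69 percentage points of power (80 − 62 and 80 − 11) at assumed within-subject correlations of 0.3 to 0.7.

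This should be corrected, because it changes which claims the study can support.

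**What to change.** 1. List HR, BLA and RPE as secondary in the SAP. Reconcile the role of ET across the primary objective, the two titles and the SAP.
2. Name one primary outcome, or a short list, chosen by the sponsor from the primary objective. With more than one, control the overall error at 0.05, for example with Holm. Keep the group × time interaction as the tested effect or say what replaces it, name the tested effect for ET if it becomes primary, and apply a sphericity correction so that each test holds its level.
3. Analyse ET with a repeated-measures ANOVA, or a mixed model with subject as a random effect.
4. Protocol section 3 describes the trials in the past tense. If outcome data have already been seen, label the choice of primary outcome post hoc.

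**Cost.** No new data, and no alpha cost with one primary outcome. Outcomes not on the list can no longer carry a primary claim. With several outcomes, the first Holm step costs power for an effect that has 80% at 0.05 (n = 16):

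| Primary outcomes | First-step level | Condition effect (3 and 45 df) | Interaction (15 and 225 df) |
|---|---|---|---|
| 2 | 0.05/2 = 0.025 | 70% | 71% |
| 4 (PP, MP, FI, ET) | 0.05/4 = 0.0125 | 60% | 61% |

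This loss is a reason to keep the list short.
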